#### 5.3.2.4 Scheduling of Specimen Collection to Foundation Medicine

Whole blood samples should be shipped the same day as collection and should be stored at ambient temperature until shipped. Do not freeze or refrigerate the samples. Samples should only be collected monday-thursday.

#### 5.3.2.5 Scheduling of Specimen Collection to the EET Biobank

Fresh blood specimens may be collected and shipped Monday through Friday.

## 5.4 Specimen Tracking System Instructions

### 5.4.1 Specimen Tracking System Overview and Enrollment Instructions

For the ETCTN STS, the following information will be requested:

- Protocol Number
- Investigator Identification
  - Institution and affiliate name
  - Investigator's name
- Eligibility Verification: Patients must meet all the eligibility requirements listed in Section 3.
- Additional Requirements:
  - Patients must provide a signed and dated, written informed consent form.

Upon enrolling a patient, IWRS will communicate with OPEN, assigning two separate and unique identification numbers to the patient, a Universal patient ID (UPID) and a Treatment patient ID. The UPID is associated with the patient and used each and every time the patient engages with the portion of this or any other protocol that uses the ETCTN Specimen Tracking System. The UPID contains no information or link to the treatment protocol. IWRS will maintain an association between the UPID for ETCTN biobanking and molecular characterization and any treatment protocols the patient participates in, thereby allowing analysis of the molecular characterization results with the clinical data.

Immediately following enrollment, the institutional anatomical pathology report for the diagnosis under which the patient is being enrolled must be uploaded into Rave. The report must include the surgical pathology ID (SPID), collection date, block number, and the IWRS-assigned UPID and patient study ID for this trial. For newly acquired biopsies without a corresponding pathology report, the radiology and operative report(s) must also be uploaded into Rave, when available. **Important:** Remove any personally identifying information, including, but not limited to, the patient's name, date of birth, initials, medical record number, and patient contact information from the institutional pathology report prior to submission.

Additionally, please note that the STS software creates pop-up windows when reports are generated, so you will need to enable pop-ups within your web browser while using the software.

For questions regarding the Specimen Tracking System, please contact STS Support at [[contact]](mailto:[contact]).

The Shipping List report **must** be included with all sample submissions.

### 5.4.2 Specimen Labeling

#### 5.4.2.1 Blood Specimen Labels

Include the following on blood specimens (including whole blood and frozen, processed blood products – like serum):

- Patient Study ID
- Universal Patient ID (UPID)
- Specimen ID (automatically generated by Rave)
- Time point
- Specimen type (e.g., blood, serum)
- Collection date (to be added by hand)

#### 5.4.2.2 Tissue Specimen Labels

[figure not shown]
Include the following on all tissue specimens (e.g., FFPE block, or frozen tissue):

- Patient Study ID
- Universal Patient ID (UPID)
- Specimen ID (automatically generated by Rave)
- Time point
- Specimen type (e.g., formalin-fixed paraffin-embedded [FFPE] Block, Formalin Fixed Tissue, Fresh Tissue in Media, etc.)
- Tissue type (P for primary, M for metastatic or N for normal)
- Surgical pathology ID (SPID) number (when applicable)
- Block number from the corresponding pathology report (FFPE tissue)
- Collection date (to be added by hand)
- Slide section number (only if archival tissue is submitted as slides) (to be added by hand)

#### 5.4.2.3 Example of Specimen Label Generated by STS

STS includes a label printing facility, accessed via the Print Label CRF in the All Specimens folder. A generated PDF is emailed to the user as a result of saving that form.

The following image is an example of a tissue specimen label printed on a label that is 0.5" high and 1.28" wide.

The QR code in the above example is for the Specimen ID shown on the second line.

Labels may be printed on a special purpose label printer, one label at a time, or on a standard

laser printer, multiple labels per page. Theradex recommends the use of these low temperature waterproof labels for standard laser printers: <https://www.labtag.com/shop/product/cryo-laser-labels-1-28-x-0-5-cl-23-colors-available/>

The last line item on the label includes the following data points joined together:

1. Tissue only: Primary (P), Metastatic (M), Normal (N) tissue indicated at the beginning of the specimen ID; this field is blank if not relevant (e.g., for blood)
2. Block ID or blank if not relevant
3. SPID (Surgical Pathology ID) or blank if none
4. An optional alpha-numeric code that is protocol specific and is only included if the protocol requires an additional special code classification

**Space is provided at the bottom of the label for the handwritten date and optional time.**  
The last line on the example label is for the handwritten date and optional time.

#### 5.4.3 Overview of Process at Treating Site

##### 5.4.3.1 OPEN Registration

All registrations will be performed using the Oncology Patient Enrollment Network (OPEN) system. OPEN communicates automatically with the Interactive Web Response System (IWRS) which handles identifier assignments, any study randomization, and any prescribed slot assignments. If specimen analysis is required to determine eligibility, the protocol will be setup with multi-step registration.

Registration without eligibility specimen analysis:

1. Site enters registration data into OPEN during one or more steps.
2. IWRS receives data from OPEN, generates the Patient Study ID and the Universal Patient ID, both of which are sent back to OPEN.
3. IWRS sends all applicable registration data directly to Rave at the end of the final registration step.

Any data entry errors made during enrollment should be corrected in Rave.

##### 5.4.3.2 Rave Specimen Tracking Process Steps

**Step 0:** Log into Rave via your CTEP-IAM account, then navigate to the appropriate participant.

**Step 1:** Complete the **Histology and Disease** form (but do not upload reports until a specimen label can be applied to them) and the Baseline forms regarding **Prior Therapies**. Enter the initial clinical specimen data:

- **Specimen Tracking Enrollment CRF:** Enter Time Point, Specimen Category, Specimen Type, Block number, Tissue type, Surgical Path ID, and number of labels needed (include extra labels to apply to reports to be uploaded). CRF generates unique

Specimen ID.

**Step 2:** Print labels using the **Print Labels** CRF located in the All Specimens folder, then collect specimen.

- Label specimen containers and write collection date on each label. After collection, store labeled specimens as described in Section 5.4.2.
- Apply an extra specimen label to *each* report before scanning. Return to the **Histology and Disease** form to upload any initial Pathology, Radiology, Bone Marrow [*if bone marrow is submitted*], Molecular Reports (up to 4), and Surgical (or Operative) reports. Return to **Specimen Tracking Enrollment** CRF to upload any molecular report (one per specimen) and/or specimen specific pathology or related report (one per specimen) and/or the Tissue Biopsy Verification form (when applicable). Uploaded reports should have protected health information (PHI) data, like name, date of birth, mailing address, medical record number or social security number (SSN), redacted. **Do not redact SPID, block number, diagnosis or relevant dates (such as collection date), and include the UPID and patient study ID on each document** (either by adding a label or hand writing).

**Step 3:** Complete specimen data entry.

- **Specimen Transmittal** Form: Enter collection date and time and other required specimen details.

**Step 4:** When ready to ship, enter shipment information.

- **Shipping Status** CRF: Enter tracking number, your contact information, recipient, number of sample containers and ship date once for the first specimen in a shipment.
- **Copy Shipping** CRF: In the specimen folders for additional specimens (if any) that will be shipped with the initial specimen, please use the **Copy Shipping** form to derive common data into additional **Shipping Status** forms. A few unique fields will still need to be entered in **Shipping Status**.

**Step 5:** Print shipping list report and prepare to ship.

- Shipping List report is available at the site level.
- Print two copies of the shipping list, one to provide in the box, the other for your own records.
- Print pathology or other required reports to include in the box. Be sure the printed copy includes the specimen label.

**Step 6:** Send email notification.

- For only one of the specimens in the shipment, click “Send Email Alert” checkbox on the **Shipping Status** CRF to email recipient.

**Step 7:** Ship the specimen(s).

**Step 8:** Monitor the Receiving Status form located in each specimen folder for acknowledgment of receipt and adequacy.

## 5.5 Specimen Collection

### 5.5.1 Archival Tumor Tissues

- a. Attempts to obtain biopsy or surgical archival tumor samples will be made for every subject. The tissue sample should have proper size to enable analysis. Request for tissue samples should begin during Screening Visit and continue to be requested until tissue sample is obtained or documentation that the sample cannot be obtained. Samples should be from the most recent biopsy or surgical resection of the original tumor (or metastatic site, if original tumor is not available).
- b. One formalin-fixed paraffin-embedded tissue block, or cut unstained slides will be requested. If sufficient tissue is available, we request 1 H&E cut at 4 micrometers, 15 unstained sections, cut at 4 micrometers and mounted in poly-l-lysine-coated or plus (+) slides.
- c. The sectioning of FFPE tissue for the immunohistochemical studies, and molecular study should be done at the same time as the standard clinical H&E section and the immunohistochemical sections to minimize tissue loss. Remaining tissue will be archived by the Pathology Department at each respective institution. FNA samples do not contain adequate material for analysis and will not be requested.
- d. The following guidelines should be used for preparation of slides:
  - i. Slides #1: to be regular 4 microns, positively charged slide, H&E, with cover
  - ii. Slides #2 and above: 4 microns, positively charged slides, unstained, NO COVER
  - iii. Blades need to be changed between blocks, if more than one block is being cut.
  - iv. If possible, slides and process need to be DNAase free and tissue should be mounted on the bottom third of the slide.

### 5.5.2 Fresh Tumor Specimens

- a. Supplies
  - i. 10% Neutral Buffered Formalin (ambient/room temperature) (VWR #16004-115)
  - ii. Cryovial tubes – 1.8 ml cryotubes/vials (e.g., Nunc Code #377267 or equivalent)
  - iii. Conical tubes – 15 mL (e.g., Sarstedt Code #62.554.001 PP or equivalent)
- b. For patients with tumor that is amenable to biopsy, core biopsies will be collected at study baseline and at cycle 1 day 21 (+/-5 days).
- c. A maximum of 5 core biopsies (or fine needle aspirates, if cores are considered unsafe) will be obtained from each subject whose tumor is amenable to undergo a biopsy.
- d. The biopsies will be used to prepare paraffin embedded and frozen samples. A total of 5 biopsies is preferred, when possible.
- e. The first pass will generally be used for on-site examination of the material, to determine presence and quality of lesional tissue.
- f. The remaining biopsy tissue will be paraffin embedded and frozen at each

respective institution.

- g. If a limited amount of tumor tissue is obtained, paraffin embedded tissue should be prioritized over frozen tissue.
- h. Archived or freshly obtained paraffin embedded formalin fixed (FFPE) or frozen tissues of biopsied specimens are needed for the purposes of:
  - i. Pathological examination (for conventional pathology examination, such as H&E stain)
  - ii. Examination of immune and inflammatory fibroblast biomarkers via IHC or IF analysis, as appropriate.
  - iii. Future analysis of genomic and transcriptome features within the tumor microenvironment.
- i. *Samples will be collected in this order:*
  - i. Core 1 – Formalin-fixed paraffin-embedded (FFPE)
  - ii. Core 2 – FFPE
  - iii. Core 3 – Snap Frozen
  - iv. Core 4 – FFPE
  - v. Core 5+ – Snap Frozen
  - vi. *For example, if only 2 cores are obtained, one core should be FFPE and one core should be snap frozen.*
- j. Formalin-Fixed Paraffin-Embedded (FFPE) Tumor Specimens guide
  - i. FFPE tumor tissue block(s) must be submitted. The optimal block is at least 70% tumor.
  - ii. Specimen size requirement is as follows:
    - 1. Surface area: 25 mm^2 is optimal. Minimum is 5 mm^2.
    - 2. Volume: 1 mm^3 optimal. Minimum volume is 0.2 mm^3, however the success of DNA extraction decreases at suboptimal tissue volume.
- k. Snap Frozen Specimens guide
  - i. The biopsy specimen should be placed in a 1.8 ml cryotubes/vials (e.g., Nunc Code #377267 or equivalent)
  - ii. Label the cryovial with the timepoint (eg pretreatment or C1D21), and subject's study ID.
  - iii. Rapidly cool - the cryovial should be cooled to -70°C (or lower) very rapidly using dry ice, a -80°C freezer, or liquid nitrogen.
  - iv. The snap frozen samples should never be thawed.

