## 5. BIOMARKER, CORRELATIVE, AND SPECIAL STUDIES

### 5.1 Summary Table for Specimen Collection

| Time Point   | Specimen   | Send Specimens To:   |
|--|--|--|
| Archival  |  |  |
|  | 
 
Formalin-fixed paraffin-embedded (FFPE) tumor tissue block (preferred) (mandatory)
 
 
If a block is not available, then submit:
 
 
1 H&E stained slide (4 <math>\mu</math>m)
 
15 unstained, 4 micron, positively charged slides, no cover
 
 | [name] Laboratory  |
| Baseline  |  |  |
|  | 
 
3 FFPE tumor tissue blocks (mandatory)
 
2 snap frozen tumor cores (mandatory)
 
  | [name] Laboratory  |
|  | 
 
8.5 mL peripheral blood in FoundationOne Liquid CDx cfDNA tubes (optional) (see Section 11 [Footnote L])
 
   | Foundation Medicine  |
|  | 
 
30 mL peripheral blood in EDTA tubes (mandatory)
 
   | [name] Laboratory  |
|  | 
 
20 mL in Streck cfDNA tube (mandatory)
 
   | EET Biobank  |
| Day 1 of Cycles 1-6, 9 and 12   |  |  |
| 
 
Pre infusion
 
30 minutes after the end of infusion of CDX-1127 (varlilumab), which will be administered after atezolizumab
 
 | 
 
6 mL Peripheral blood in red-top tube processed for serum and frozen (mandatory)
 
   | OSU Comprehensive Cancer Center (OSUCCC) Pharmacoanalytical Shared Resource (PhASR) Laboratory |
| Day 15 of Cycles 1 and 2  |  |  |
| 
 
Pre infusion
 
30 minutes after the end of infusion of CDX-1127 (varlilumab), which will be
 
                                 | 
 
6 mL Peripheral blood in red-top tube processed for serum and frozen (mandatory)
 
   | OSU Comprehensive Cancer Center (OSUCCC) Pharmacoanalytical Shared Resource (PhASR) Laboratory |

|  |   |                     |
|--|---|---------------------|
| administered
after
atezolizumab) |   |                     |
| Cycle 1 Day 21                  |   |                     |

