|  | 
 
• 3 FFPE tumor tissue blocks (mandatory)
 
• 2 snap frozen tumor cores (mandatory)
 
 | [name] Laboratory |
|  | 
 
• 30 mL peripheral blood in EDTA tubes (mandatory)
 
  | [name] Laboratory |
|  | 
 
• 20 mL in Streck cfDNA tube (mandatory)
 
  | EET Biobank         |
| Week 12 (End of Cycle 3)        |   |                     |
|  | 
 
• 30 mL peripheral blood in EDTA tubes (mandatory)
 
  | [name] Laboratory |
| End of Treatment (EOT)          |   |                     |
|  | 
 
• 30 mL peripheral blood in EDTA tubes (mandatory)
 
  | [name] Laboratory |
|  | 
 
• 20 mL in Streck cfDNA tube (mandatory)
 
  | EET Biobank         |

See Sections [5.2](#) and [5.5.2](#) for priority of cores.

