## 5.2 Summary Table(s) for Interventional Radiologist for Research Biopsies

| Biopsy #: 1  |                  |   |                        |                        |
|---|------------------|---|------------------------|------------------------|
| Trial Time Point: Baseline   |                  |   |                        |                        |
| IR Biopsy Definition: Research – No Clinical Impact (All cores from a single biopsy procedure impact research goals, but do not directly impact patient care or benefit the patient. |                  |   |                        |                        |
| Core Priority   | Use in the Trial | Biomarker Name(s)   | Tumor Content Required | Post-Biopsy Processing |
| 1   | Integrated       | CD8+T effector cells  | ≥10%                   | FFPE                   |
| 2   | Exploratory      | PD-L1 expression on tumor and tumor infiltrating lymphocytes (TILs) | ≥10%                   | FFPE                   |

|     |             |   |             |             |
|-----|-------------|---|-------------|-------------|
| 3   | Exploratory | Analysis of tumor microenvironment examining changes to focused tumor immune infiltrating lymphocyte populations by multiplex IHC | $\geq 10\%$ | FFPE        |
| 4-5 | Exploratory | Analysis of expression of immune-related pathways in the tumor microenvironment by RNA seq  | $\geq 10\%$ | Snap Frozen |

| Biopsy #: 2  |                  |   |                        |                        |
|---|------------------|---|------------------------|------------------------|
| Trial Time Point: Cycle 1, Day 21  |                  |   |                        |                        |
| IR Biopsy Definition: Research – No Clinical Impact (All cores from a single biopsy procedure impact research goals, but do not directly impact patient care or benefit the patient. |                  |   |                        |                        |
| Core Priority   | Use in the Trial | Biomarker Name(s)   | Tumor Content Required | Post-Biopsy Processing |
| 1   | Integrated       | CD8+T effector cells  | $\geq 10\%$            | FFPE                   |
| 2   | Exploratory      | PD-L1 expression on tumor and tumor infiltrating lymphocytes (TILs)   | $\geq 10\%$            | FFPE                   |

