| N: Baseline scans must be done <4 weeks prior to randomization. Tumor measurement will be performed with contrast CT chest/abdomen/pelvis. Non-contrast CT chest/abdomen/pelvis or CT Chest and MRI Abdomen/pelvis will be performed in subjects with contraindications or intolerance to contrast dye. For the first on-treatment scan, this should be done approximately 8 weeks from the start of treatment (not from the date of the pre-treatment baseline scan). Imaging will be repeated every 8 weeks, irrespective of dosing schedule or treatment delays. For the End of Treatment visit, scans do not need to be repeated if a scan has been performed within 8 weeks. For patients removed from study treatment for reasons other than progression, scans are to continue every 8 weeks until progression. |                                    |                      |         |        |        |         |       |        |                    |        |       |  |        |        |
| O: CA19-9 does not need to be repeated in the event that the screening lab draw show that the patient's tumor does not secrete CA19-9.   |                                    |                      |         |        |        |         |       |        |                    |        |       |  |        |        |
| P: Only for subjects with tumor that in the opinion of the study treatment team is safely accessible for biopsy. See Section 5.5.2 for the order of the tumor cores to be collected. The baseline biopsy is to be done after randomization but before C1D1.  |                                    |                      |         |        |        |         |       |        |                    |        |       |  |        |        |
| Q: Blood collection will be collected at baseline, C1D21, and Week 12 (end of Cycle 3). Pre-treatment baseline EDTA and Streck tube draws should only be drawn on enrolled patients and can be drawn anytime between time of enrollment and prior to start of treatment. These samples must be collected only Monday - Thursday and shipped overnight same day. See Section 5.1 for more details.  |                                    |                      |         |        |        |         |       |        |                    |        |       |  |        |        |

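### Sections 5.2 and 5.5.2 give conflicting biopsy core orders, so at a yield of 2 or 3 cores PD-L1 or multiplex IHC can lose its core to RNA-seq; the status of the on-site first pass is also unstated

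*Combined protocol and SAP*

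**What the plan says.** Section 5.1 makes three FFPE blocks and two snap-frozen cores mandatory at baseline and again at Cycle 1 Day 21. Its footnote sends sites to both Section 5.2 and Section 5.5.2 "for priority of cores". Footnote P of the Study Calendar (Section 11) names only one of them: "See Section 5.5.2 for the order of the tumor cores to be collected".

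Section 5.2 gives the same ranking at both time points: core 1 FFPE for CD8+ (the integrated marker), core 2 FFPE for PD-L1, core 3 FFPE for multiplex IHC, cores 4 and 5 snap frozen for RNA-seq. The tissue part of the Section 5.8 biomarker table ranks the four assays in that same order.

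Section 5.5.2 contains these rules:
- Item (c) caps the biopsy at 5 cores.
- Item (e): "The first pass will generally be used for on-site examination of the material, to determine presence and quality of lesional tissue".
- Item (f) has the tissue left over embedded and frozen.
- Item (g), for limited tissue: "paraffin embedded tissue should be prioritized over frozen tissue".
- Item (i) lists core 1 FFPE, core 2 FFPE, core 3 snap frozen, core 4 FFPE, and core 5 onward snap frozen. It ends with the example: "For example, if only 2 cores are obtained, one core should be FFPE and one core should be snap frozen".

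**The concern.** A site with a partial yield has two authorised sources for what to do with it, and they disagree. One of them also disagrees with itself. Two sites with the same number of cores can each follow the protocol and keep different tissue.

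Low yield is expected here. Section 2.4.5 says that enough biopsy tissue is often hard to obtain in biliary cancer, and Section 2.3.1 describes only a limited number of paired biopsies in the predecessor trial. The rules for 2 or 3 cores are therefore likely to be used.

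What is at stake is correlative. PD-L1 and multiplex IHC feed the paired baseline and on-treatment comparisons of Section 9.4.1. The change in CD8+ density is the correlative secondary endpoint compared between arms in Section 9.4, and it needs usable FFPE tissue at both time points. The core order bears on the first two. Only the unclear status of the on-site pass bears on CD8+.

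**Working it through.** **Inputs.** Mandatory specimens per biopsy: 3 FFPE and 2 frozen (5.1). Maximum cores: 5 (5.5.2(c)). Order in 5.2: F, F, F, S, S. Order in 5.5.2(i): F, F, S, F, S. Example for 2 cores: one F, one S. (F = FFPE, S = snap frozen.)

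**The plan's own total.** 3 + 2 = 5, which equals the cap. Taken to 5 cores, both orders give 3 FFPE and 2 frozen, so at full yield the sections are consistent.

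**Allocation by number of usable cores k.** Count F and S in the first k places of each order (FFPE/frozen):

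| k | 5.2 order | 5.5.2(i) list | 5.5.2(i) example |
|---|---|---|---|
| 1 | 1/0 | 1/0 | none given |
| 2 | 2/0 | 2/0 | 1/1 |
| 3 | 3/0 | 2/1 | none given |
| 4 | 3/1 | 3/1 | none given |
| 5 | 3/2 | 3/2 | none given |

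- At k = 2 the list agrees with 5.2 and only the example differs. It replaces the second FFPE core, which 5.2 assigns to PD-L1, with a frozen core for RNA-seq.
- At k = 3 the list replaces the third FFPE core, which 5.2 assigns to multiplex IHC, with a frozen core for RNA-seq.
- At k = 1, 4 and 5 there is no difference.
- Every row and the example contain at least one FFPE core, and CD8+ is priority 1. The order conflict alone therefore leaves the CD8+ core in place.

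**On-site first pass.** Suppose, which the text does not settle, that this pass counts within the 5 and is consumed.

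- Cores left: 5 - 1 = 4. Specimens required: 3 + 2 = 5. Shortfall: 1.
- If the 5.5.2(i) numbering restarts after the on-site pass, the 4 left are F, F, S, F: 3 FFPE and 1 frozen.
- If the on-site pass is itself core 1, cores 2 to 5 are F, S, F, S: 2 FFPE and 2 frozen. An IHC core is lost and RNA-seq keeps both of its cores.
- With a single pass, 1 - 1 = 0, so no CD8+ tissue remains. With two passes handled as in the example, the same happens if the FFPE core is the one examined on site.

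If instead the on-site pass is additional to the 5, or the examined tissue is embedded afterwards, the 3 + 2 requirement can be met in full.

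**The case against.** The best case for leaving the text alone has four parts.

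First, item (g) already breaks the tie in favour of paraffin when tissue is limited. It does show the intended direction, and it agrees with 5.2 and 5.8. But the example addresses the 2-core case by name and says the opposite, and a site will tend to follow the specific instruction. The point stands.

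Second, RNA-seq is marked mandatory in Section 5.8, so holding back a frozen core may be deliberate. That is possible. If so, 5.2, 5.8 and item (g) are the passages that need changing, because all three put frozen tissue last.

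Third, losing a dedicated core need not mean losing the result. Section 2.4.3 has stains chosen in priority order according to the tissue obtained, and its multispectral platform reads 12 markers on one FFPE section. A reader might infer that PD-L1, multiplex IHC or the CD8-to-FoxP3 ratio becomes unobtainable. The documents do not support that. They also give no rule for sharing a fresh core, and 5.2 assigns one core to each assay. What can be said is that the assigned core is diverted.

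Fourth, the 4-against-5 shortfall is not certain. Item (e) is qualified, it does not say the tissue is used up, item (d) intends the biopsies for embedded and frozen samples, and item (i) assigns every core, including core 1, to FFPE or freezing. This objection succeeds against any flat statement that the mandatory set cannot be met. What survives is that the text leaves the question open.

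**Conclusion.** This is an internal inconsistency that should be corrected, and its reach is narrow. It diverts one core from a higher-ranked IHC use to RNA-seq in two situations: the PD-L1 core at 2 cores if the example is followed, and the multiplex IHC core at 3 cores if the 5.5.2 list is followed. This count rests only on the orders as printed.

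The on-site pass is a separate gap in the text. The shortfall of one specimen, and the possibility that a 1-core patient has no CD8+ tissue, hold only if that pass both counts within the 5 and is consumed.

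A reader might infer that the conflicting orders put the CD8+ secondary endpoint at risk. They do not: the first allocated core is FFPE in both lists and the example keeps one FFPE core. The documents give no yield distribution, so the number of patients affected cannot be estimated. ORR, PFS, sample size and power are untouched.

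**What to change.** - In 5.5.2(i), replace the list with the order already in 5.2 and 5.8: cores 1 to 3 FFPE, cores 4 and 5 snap frozen.
- Delete the 2-core example, or make it two FFPE cores.
- In 5.5.2(e), state whether the on-site pass counts within the 5 cores. State also that the examined tissue is kept for FFPE where possible, so that it does not displace the CD8+ core.

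After the change, k usable cores give the smaller of k and 3 FFPE cores: 2 at k = 2 (the example now gives 1) and 3 at k = 3 (the list now gives 2).

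The references in the 5.1 footnote and in calendar footnote P can then stay as they are, because both sections would say the same thing. The cost is protocol wording, with no added cores or procedures. The downside is less snap-frozen tissue for exploratory RNA-seq when the yield is low, which item (g) already accepts.
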